**1. Determine the efficacy of an adaptive progressive VI reinforcement intervention for reducing cocaine use in the short- and long-term.** The hypothesis is that patients assigned to the adaptive progressive VI reinforcement intervention will achieve longer periods of abstinence than patients in standard care during the period reinforcement is in effect (24 weeks). We will also evaluate how well this reinforcement intervention maintains benefits throughout follow-up (18 months).

**2. Compare the relative efficacy of adaptive progressive VI reinforcement to a traditional reinforcement intervention.** Patients receiving adaptive progressive VI reinforcement are hypothesized to achieve greater during and post-treatment abstinence than those receiving traditional twice-weekly reinforcement.

Secondary and exploratory aims of the study are to:

**a. Evaluate relations between behavioral and measures of cognitive control and response to monetary rewards and treatment outcomes.** Patients with better cognitive control are expected to achieve longer durations of abstinence, regardless of treatment assignment. Patients who are more sensitive to monetary rewards are expected to achieve longer duration of abstinence, particularly when assigned to a reinforcement intervention. We also expect that sensitivity to monetary rewards and cognitive control may increase among those who are assigned to a reinforcement intervention, and that changes in these processes may mediate drug use outcomes.

**b. Assess the impact of reinforcement interventions on HIV risk and other outcomes.** Compared to SC, reinforcement interventions are expected to reduce high risk sexual behaviors that spread infectious diseases. Reinforcement interventions are also hypothesized to decrease psychiatric symptoms and improve quality of life. Both short-term and long-term effects will be examined. Gender effects will also be explored.

**c. Estimate costs and cost-effectiveness.** We will examine costs and cost-effectiveness of interventions and estimate conditions under which, and patients for whom, these interventions may be most cost-effective.

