*b.) Response to monetary rewards.* Contemporary theories on addiction point to abnormalities in reward circuitry in regions such as the ventral striatum and ventromedial prefrontal cortex (e.g., Chau et al., 2004; Volkow et al., 2003). Volkow et al. (2003) have proposed that, in addiction, the reward value of drugs increases while the reward value of other reinforcers (such as money) decreases. Many studies have shown deficits in reward processing, reflected by reduced response to monetary rewards in the ventral striatum, in substance using patients relative to healthy controls (Balodis et al, 2012; Beck et al, 2009; Peters et al, 2011; Wrase et al, 2007). These findings appear especially relevant to reinforcement interventions, because they provide monetary rewards as alternatives to those derived from drugs. By their nature, these interventions may be particularly beneficial for those who are sensitive to monetary rewards. Therefore, we expect that individuals' neurocognitive responses to monetary rewards pre-treatment may predict treatment outcomes in reinforcement conditions, serving as a potential moderator of treatment effects. Further, because monetary rewards appear to serve as effective reinforcers at least as long as they are in effect, we expect that sensitivity to monetary rewards may increase during treatment, and that this increase may mediate outcomes.

**5. Cost-effectiveness.** We will not only evaluate the efficacy and moderators and mediators of these interventions, but also their cost-effectiveness, as we have done previously (Olmstead et al. 2007abc, 2009). These data will help inform decisions about for whom and under what circumstances funders or society may be willing to pay for their increased costs. As more private providers, state systems (NY, SC), and federal agencies (the VA) are integrating these interventions, this study will provide important and timely data regarding the conditions under which and patients for whom reinforcement interventions engender benefits.

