We have fMRI pilot data from Carroll et al.'s (under review) trial relevant to reinforcement interventions. Pre- and post-treatment imaging data from the Stroop task (described in DeVito et al., 2012) were obtained from 22 cocaine dependent patients. Eleven were randomized to a reinforcement intervention, and 11 to a non-reinforcement intervention; all 22 received placebo medication. Two main findings emerged: 1) Greater pre-treatment Stroop activity in the dorsolateral prefrontal cortex (dlPFC) was positively correlated with reinforcers earned in those receiving the reinforcement intervention, suggesting that better cognitive-control pre-treatment may be related to better response to treatment (Fig 1). 2) Stroop activity decreased in dmPFC and dlPFC from pre- to post-treatment in those receiving the reinforcement intervention, and these effects were greater among those in the reinforcement than the non-reinforcement condition (Fig 2). We reported similar decreases in these regions in concert with improvements in Stroop performance, suggesting greater efficiency in these PFC circuits (DeVito et al., 2012) and consistent with findings noted with working memory training (Klingberg, 2010). Together, these data suggest that Stroop-related activation in the PFC may relate to outcomes, and that reinforcement interventions may be associated with changes in brain functioning in these

[figure not shown]

regions.

The Monetary Incentive Delay (MID) task is commonly used to assess neural activity during anticipation and receipt of monetary rewards (Balodis et al., 2012). Neural activity is compared between no reward (\$0) and reward conditions (\$5) during a period of anticipation, and once the outcome is revealed (winning \$5 or \$0). Compared to controls, those with drug use disorders have reduced neural response to monetary rewards in regions including the ventral striatum (VS; Andrews et al., 2011; Balodis et al., 2012; Goldstein et al., 2007). MID data are available from the 11 cocaine-dependent participants above who received a reinforcement intervention. As expected, greater pre-treatment activity in the VS during receipt of monetary rewards (outcome phase) was associated with longer abstinence during treatment (Fig 3). We also observed increases in activity in the VS pre- to post-treatment in patients receiving the reinforcement intervention (Fig 4).

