The fMRI sub-study will provide refined tests of hypotheses related to cognitive control in a subsample. The Stroop effect is calculated as the difference in reaction time between incongruent and congruent trials. In fMRI data, it is defined as difference in neural activity between incongruent and congruent trials.

1. To evaluate relationships between pre-treatment behavioral and neural measures of cognitive control during the Stroop task and treatment outcome, we will assess the Stroop effect and related neural activity and correlate these indices with treatment outcomes (e.g., longest duration of abstinence, % negative urines).
2. To assess changes in behavioral and neural measures of cognitive control, we will compare indices pre- to post-treatment (e.g., (Incongruent(pre) > congruent (pre)) > (Incongruent(post) > congruent (post))). We will also compare these indices between groups to identify treatment-specific changes.

The MID task allows examination of neural activity during anticipation and receipt of monetary rewards. Anticipation of reward is assessed by comparing neural activity during the reward anticipation phase, and contrasting conditions of \$0 and \$5 (Anticipation of \$5>\$0). Responses to receipt of monetary rewards are assessed by comparing neural activity during the outcome phase (Receipt of \$5>\$0).

1. To examine relationships between pre-treatment behavioral and neural measures of reward processing and treatment outcome, we will assess neural responses during anticipation and receipt of reward (\$5>\$0) and correlate these indices with treatment outcomes (longest duration of abstinence, % negative urines).
2. To evaluate the change in response to monetary rewards from pre- to post- treatment, we will compare indices from this task from pre- to post-treatment (e.g., anticipation of \$5 pre>post, and receipt of \$5 pre>post). We will also compare differences in these indices between groups to identify treatment-specific changes.

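### For the pre-treatment MID reward indices, the fMRI plan specifies only a correlation with outcome, which does not test the stated hypothesis that reward response moderates the treatment effect

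*Combined protocol and SAP*

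**What the plan says.** **Hypothesis.** Specific aims, secondary and exploratory aim a: "Patients who are more sensitive to monetary rewards are expected to achieve longer duration of abstinence, particularly when assigned to a reinforcement intervention". Innovation, item 4b, makes the neural version explicit. Pre-treatment response to monetary rewards may predict outcome in the reinforcement conditions, "serving as a potential moderator of treatment effects". The Preliminary studies section closes by saying that the trial will look at these associations with standard care patients as comparators. It gives no method.

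**Analysis of pre-treatment indices.** In the Data Analysis text on the fMRI sub-study, MID item 1 takes neural response in the anticipation and receipt phases, each as 5-dollar against 0-dollar trials, and will "correlate these indices with treatment outcomes (longest duration of abstinence, % negative urines". It does not say whether the correlation is pooled or by arm. It gives no arm term, no interaction and no comparison of correlations.

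**Analysis of change.** For MID item 2, "we will compare indices from this task from pre- to post-treatment". A bracketed example follows that shows the 5-dollar condition, written pre>post. Item 2 then adds a between-group comparison, which concerns change in the indices and not their association with outcome.

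**General moderator text.** Elsewhere in Data Analysis, moderators are to be explored in general terms, with gender named. The predictor regressions are to be run with interactions by condition. The cognitive predictors listed there are baseline computer-task and impulsivity scores.

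**Size.** Thirty patients per group, in Groups A and C only, are said to suffice for correlations of at least .30.

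**The concern.** A moderator claim is a claim about a difference: the slope of outcome on reward response is steeper under reinforcement than under standard care. A correlation estimates something else. Pooled over arms, it mixes the two slopes, so it shrinks when only one arm carries the association and is largest when both do. Computed within each arm, it invites the reader to compare two p-values, which is not a test of the difference.

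The protocol says that, if cognitive control moderates the effect, future work may direct these interventions to the patients most likely to benefit. It also anticipates cost-effectiveness analyses in patients with greater reward sensitivity, should that prove an important predictor of response. Both uses need evidence that the treatment effect varies with the index. A significant correlation shows only that the index predicts outcome.

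**Working it through.** **Inputs from the plan.** 30 patients per arm in Groups A and C; target r = .30. Alpha .05 and power 0.80 are stated for the primary aims only, and sidedness is not stated; two-sided .05 and 0.80 are assumed here.

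**Assumed inputs.** The documents give no correlations by arm, so several pairs are used. The 0.6 SD arm difference in outcome is the low end of the during-treatment effect sizes quoted in the power section.

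**Step 1: the plan's own figure.** By Fisher's z, n = ((1.960 + 0.842)/atanh(.30))² + 3 = (2.802/0.3095)² + 3, which rounds up to 85 (68 one-sided). Power at r = .30:
- n = 30: Φ(0.3095 × √27 − 1.960) = Φ(−0.352) = 0.36
- n = 60: Φ(0.3095 × √57 − 1.960) = Φ(0.377) = 0.65

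The stated figure is not reproduced at 80% power. The value .30 lies close to the one-sided significance threshold at n = 30 (.306), where power is about 50%. That is a separate matter; it is shown because the 0.36 is needed in step 3.

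**Step 2: pooled correlation.** Take r = .30 in C and 0 in A, with within-arm SD 1. The average covariance is (.30 + 0)/2 = .15. The arm difference adds (0.6/2)² = 0.09 to the outcome variance. Pooled r = .15/√1.09 = .144, and power is Φ(atanh(.144) × √57 − 1.960) = Φ(−0.87) = 0.19. A simulation of 4,000 samples gave a mean r of .14, significant in 19.9%. With r = .30 in both arms and no arm difference in outcome, the pooled correlation was significant in 65% of simulated samples. It is thus significant more often where there is no moderation than where there is.

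**Step 3: separate correlations.** With r = .30 in both arms, the chance of significance in C and not in A is 0.363 × (1 − 0.363) = 0.231. In the same setting an index-by-arm test rejected in 4.6% of 4,000 simulated samples, near its nominal 5%.

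**Step 4: power of the interaction test, 30 per arm.** For the difference of two Fisher z values, SE = √(2/27) = 0.272, and power = Φ(difference/SE − 1.960).

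| r in C vs A (assumed) | Difference in z | Power | n per arm for 80% |
|---|---|---|---|
| .30 vs 0 | 0.310 | 0.205 | 167 |
| .50 vs .10 | 0.449 | 0.378 | 81 |
| .50 vs 0 | 0.549 | 0.523 | 56 |

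Simulating the linear model with an interaction term gave 20.6% and 50.6% for the first and third rows. The smallest contrast with 80% power has a z difference of 2.802 × 0.272 = 0.762, that is r = .64 against 0.

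**The case against.** **The intent to compare arms is stated.** Preliminary studies promises the comparison, Data Analysis says that moderators will be explored, and the predictor regressions carry interactions with condition. Their predictor list is introduced in a way that need not be exhaustive. This stands against any claim that moderation cannot be tested: both arms are scanned and the data allow it. It does not supply the missing analysis, because no sentence says how a neural index enters a model with arm.

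**Aim a is wider than imaging.** Its reward-sensitivity sentence does not mention neural measures. Delay and probability discounting and the gambling task are collected in the main study, where condition interactions are planned. This is correct and confines the point to the neural indices, where Innovation 4b places the moderator hypothesis in tentative terms.

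**The proposed test is weak.** For .30 against 0 the interaction has about the same chance of significance as the pooled correlation, roughly 20%. True: the gain is a correct target, not more power. The 23% in step 3 also describes a misreading that the plan does not itself propose. Sizing by group suggests within-arm correlations, which makes the pooled case less apt but leaves the misreading open.

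**A stronger reading of the change analysis is tempting.** A reader might infer from the bracketed MID example that the 0-dollar control is dropped and that the contrast looks for a decrease. The protocol says "we expect that sensitivity to monetary rewards may increase during treatment", and of the pilot, "We also observed increases in activity in the VS pre- to post-treatment in patients receiving the reinforcement intervention". The documents do not support that inference. The example is only illustrative, it follows indices already defined against 0-dollar trials, and no one-sided test is stated for the imaging data. A two-sided comparison would detect an increase. What remains is a wording ambiguity.

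**Conclusion.** The point holds in a limited form. For pre-treatment MID indices the plan names a moderator hypothesis and specifies an analysis that does not test it. The test is unspecified, not impossible.

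Under the assumed correlations, the pooled result is significant about 20% of the time when the association is confined to Group C, and 65% when it is equal in both arms (61% with the 0.6 SD arm difference: r = .30/√1.09 = .287, power Φ(0.27) = 0.61). Separate correlations give the misleading pattern of significance in C only about 23% of the time when nothing is moderated. These figures rest on 30 scanned patients per arm with usable data, two-sided .05 and approximately normal outcomes.

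The point concerns an exploratory aim in a 60-patient sub-study and has no bearing on the primary comparisons. The between-arm comparison of change is already planned and needs no correction beyond wording.

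**What to change.** For each pre-specified MID index (phase and region named in advance), replace the simple correlation with a regression in Groups A and C:

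- **Moderator test, exploratory:** outcome = index + arm + index × arm. Report the interaction estimate with its confidence interval.
- **Predictor test:** the index slope from the model with index and arm but no interaction, with its interval.

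State beside these analyses that the interaction has about 20% power for .30 against 0 and about 50% for .50 against 0, so that a non-significant interaction is not evidence of no moderation.

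As a wording note only, write the change example as (5-dollar minus 0-dollar) at post against (5-dollar minus 0-dollar) at pre, two-sided. This matches the index definition and allows for the hypothesised increase.

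The cost is a few lines of analysis-plan text. Scans, patients and outcomes stay the same. The price is an imprecise interaction estimate that has to be reported as such.

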These data suggest that reward-related activation in the ventral striatum, which has been implicated in drug effects and reward processing more generally, may predict treatment outcomes in

reinforcement interventions, and these interventions may be associated with increased sensitivity to monetary rewards over time. These data, however, are from a small sample, and MID data were only available from participants randomized to the reinforcement intervention (Unfortunately, multiple subjects assigned to the non-reinforcement intervention experienced technical difficulties or excessive movement during participation in the MID task, problems we have since corrected). The proposed study will examine these associations with an adequately powered sample, comparing patients receiving reinforcement and standard care interventions.

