## Methods

**Design:** This 3-group randomized design will address two primary scientific questions: (1) will adaptive progressive VI reinforcement improve short- and long-term abstinence outcomes compared to standard care, and (2) will adaptive progressive VI reinforcement yield benefits beyond that of traditional reinforcement?

**Subjects and setting:** Patients will be recruited from admissions to intensive outpatient care at Alcohol & Drug Recovery Centers (Hartford, CT), Hospital of Central CT and Farrell Center (both New Britain, CT), Carlson Recovery Centers (Springfield, MA), Regional Network of Programs (Bridgeport, CT), and The Village (Hartford, CT). Use of multiple clinics enhances generalization of findings and has worked well (Petry et al., 2011a, 2012ab). Clinics provide comprehensive services, including intensive day programs and long-term aftercare. They were selected because they have similar treatment approaches and intensities of care, and treat analogous populations.

A subset of patients assigned to SC and SC+adaptive VI reinforcement groups (n=30 per group) who do not meet exclusion criteria for imaging will be offered participation in an fMRI sub-study. Pre- and post-treatment scans will be conducted at Hartford Hospital Institute of Living's Olin Neuropsychiatry Research Center.

Inclusion criteria: Each subject must: (1) be age  $\geq$  18 years, (2) have a current DSM-5 cocaine use disorder diagnosis, and (3) be willing to sign informed consent and able to pass an informed consent quiz.

Exclusion criteria: are (1) serious, uncontrolled psychiatric illness (e.g., schizophrenia, bipolar disorder, or suicide risk), (2) in recovery from pathological gambling, or (3) do not speak English.

Exclusion criteria for the fMRI sub-study are: (1) current use of any medication that affects blood flow (e.g., for hypertension) and (2) any conditions that are contra-indicated for fMRI scanning: claustrophobia, presence of ferromagnetic metallic implants, prior severe head trauma, color blindness, left handedness and pregnancy (assessed via urinalysis on day of scanning). See Human Subjects.

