**Power analyses for primary aims.** Our studies reinforcing abstinence generally find Cohen's  $d$  effect sizes of 0.6 to  $> 1.0$  for during treatment drug use outcomes (Petry et al, 2000, 2002,2004,2005abc,2006a, 2007a,2010b,2011a,2012abc). In terms of post-treatment effects, our ongoing study is finding an effect size of 0.46 for a 12-week reinforcement intervention in enhancing post-treatment abstinence relative to standard care. Although we expect a larger effect size when 24 weeks of reinforcement is provided, and especially if more patients engage in the adaptive progressive VI reinforcement intervention for greater durations, we will conservatively power this study to detect a similar effect size of 0.46 between the VI reinforcement intervention and standard care for long-term outcomes. Using a Type I error rate of  $\alpha=.05$ , a Type II error rate of  $\beta=.20$ , and power=0.80 (Cohen, 1988), 60 patients/ group are needed to detect  $d=0.46$  between the standard care and reinforcement interventions (Aim 1). For Aim 2, the study is powered to detect a lower, but still clinically meaningful, effect size of 0.35 between the two active reinforcement conditions, similar to effect sizes found between reinforcement conditions in other studies (Petry et al., 2004, 2006a). Using the same power analyses outlined above, 110 patients/group are needed to detect  $d \geq .35$  between the traditional and adaptive reinforcement conditions with respect to during treatment and long-term outcomes. Thus, we will recruit 280 patients (60 in standard care and 110 each for the reinforcement interventions).

**Secondary aims** are to evaluate if reinforcement improves other indices of drug use, psychosocial functioning (ASI, BSI scores), quality of life, and HIV risk behaviors, as found in other studies (Ghitza et al., 2008; Hanson et al, 2008; Petry et al., 2007b,in press b). These are continuous measures, with missing data likely. If no systematic differences in missing data are noted (the case in our prior studies), hierarchical linear models (HLM; Gibbons et al., 1993) using MIXREG (Hedeker, 1993) will analyze differences between groups over time. These analyses have advantages over repeated measures ANOVA as they estimate missing data via model parameter

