For cost and feasibility issues, the fMRI study is limited to patients in groups most likely to show treatment differences, Groups A and C. This design most cost-effectively addresses the issue of if, and how, the availability of monetary based reinforcers alter brain functioning. Based on our earlier work (Devito et al., 2012; Kober et al., 2010) and pilot data, we estimate a medium effect size for changes in regions such as VS and PFC regions. Thirty participants per group is sufficient to determine correlations of  $r \geq .30$  between neural activity in Stroop and MID task and outcome variables. We estimate 25 participants post treatment will be sufficient to assess treatment-related changes in neural activity over time (see Devito et al., 2012).

If effects of reinforcement interventions are moderated by cognitive control, future studies may target these interventions toward patients based on cognitive functioning. As reinforcers add known costs, being able to determine those who will be most positively affected will help direct scarce resources toward patients most likely to benefit. If cognitive function mediates outcomes, future research may refine and test therapies that reduce impulsive choices, and improve cognitive flexibility, inhibition and/or control (Bickel et al., 2011). Combining reinforcement with an intervention that improves cognitive control may result in even more durable effects, which may reduce personal-- and societal—harms related to drug abuse.

**Economic Evaluation.** If primary hypotheses are supported, we will conduct cost-benefit analyses. These interventions can be costly, even when reinforcers are relatively modest. Not only must costs of reinforcers be included, but so must administration costs, which include staff time for managing and delivering reinforcers. Despite costs, these interventions may provide benefits to (1) clinics in terms of enhanced reimbursements (Lott & Jencius, 2009), and (2) society in terms of reductions in healthcare services (hospitalizations, ER visits) and criminal justice system costs, and improvements in workplace productivity (Petry et al., in press c). Using data from the PAC-SAT, this study will determine the net benefit of adding reinforcers, from both clinic and societal perspectives. It will also estimate costs of each week of abstinence attributable to the reinforcement conditions.

- a. Comprehensive administrative costs of interventions will be quantified (Olmstead et al., 2007abc;

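### The fMRI sub-study calls 30 per group sufficient for correlations of .30 or more, but power for a true r of .30 is only 36% to 49% within a group and 65% to 76% pooled over both

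*Combined protocol and SAP*

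**What the plan says.** Methods, Subjects and setting, sets the size of the imaging sub-study: "A subset of patients assigned to SC and SC+adaptive VI reinforcement groups (n=30 per group"), so 60 in all, which the assessment schedule confirms.

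The Data Analysis section describes the tests. For the Stroop task, "we will assess the Stroop effect and related neural activity and correlate these indices with treatment outcomes"; a parallel analysis is planned for the monetary incentive task. Neither description says whether the correlation is computed within each group or over both together.

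The size is then justified in one sentence: "Thirty participants per group is sufficient to determine correlations of" r ≥ .30 between neural activity on the two tasks and the outcome variables. No alpha, sidedness, power or calculation accompanies it.

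Preliminary studies, after conceding that the pilot was small, says: "The proposed study will examine these associations with an adequately powered sample, comparing patients receiving reinforcement and standard care interventions".

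Specific aims places this work under the heading "Secondary and exploratory aims of the study are to".

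**The concern.** Thirty observations is few for a correlation as modest as .30, so a claim of sufficiency needs a calculation behind it, and none is given. If the claim is wrong, the likely result of a real correlation of that size is a non-significant test. A reader who has been told that the sample is sufficient, and adequately powered, could take that as evidence that neural response does not predict outcome. The plan says it may use findings on moderation by cognitive control to decide which patients future work targets, so an over-read null result would have some practical weight.

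**Working it through.** **Inputs**

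- n = 30 per group, 60 pooled (Methods, Subjects and setting; assessment schedule).
- True r = .30, the smallest value the plan says it can determine (Data Analysis, fMRI sub-study).
- Alpha .05 and power .80: assumed. The plan gives them only under Power analyses for primary aims ("Using a Type I error rate of" .05, with power .80), and there without sidedness. One- and two-sided results are therefore both shown.
- No adjustment for several regions or tasks and no loss of scans. Either would lower power.

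**Reproducing the plan's figure.** No formula is given, so the required n was computed directly by the Fisher z method:

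n = ((z_alpha + z_power) / atanh(r))² + 3, with atanh(.30) = 0.3095 and z_power = 0.842.

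- Two-sided: ((1.960 + 0.842) / 0.3095)² + 3 = 84.9, so 85.
- One-sided: ((1.645 + 0.842) / 0.3095)² + 3 = 67.5, so 68.

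Neither 30 nor 60 is reproduced.

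**Power at the planned n.** Power = Φ(atanh(r)·√(n − 3) − z_alpha), plus the negligible opposite tail when two-sided.

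- n = 30: 0.3095 × √27 = 1.608. Two-sided Φ(1.608 − 1.960) = 0.363; one-sided Φ(1.608 − 1.645) = 0.485.
- n = 60: 0.3095 × √57 = 2.337. Two-sided Φ(2.337 − 1.960) = 0.647; one-sided Φ(2.337 − 1.645) = 0.756.

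**Cross-checks at true r = .30, alpha .05**

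| Method | n=30 two-sided | n=30 one-sided | n=60 two-sided | n=60 one-sided |
|---|---|---|---|---|
| Fisher z | 36.3% | 48.5% | 64.7% | 75.6% |
| Exact bivariate normal | 37.1% | 49.7% | 65.4% | 76.3% |
| Noncentral t, predictor fixed | 38.3% | 51.4% | 66.8% | 77.7% |

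Simulation (200,000 runs each) agrees with the exact row to about 0.1 point. No cell reaches 80%.

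**Smallest r detectable with 80% power.** r = tanh((z_alpha + z_power) / √(n − 3)).

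- n = 30: tanh(2.802 / 5.196) = .49 two-sided; tanh(2.486 / 5.196) = .45 one-sided.
- n = 60: tanh(2.802 / 7.550) = .35 two-sided; tanh(2.486 / 7.550) = .32 one-sided.

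**The other possible meaning: an observed r of .30 is significant.** t = r·√(n − 2) / √(1 − r²).

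| n | t | p two-sided | p one-sided | Critical r two-sided | Critical r one-sided | 95% CI for observed .30 |
|---|---|---|---|---|---|---|
| 30 | 1.66 | .107 | .054 | .361 | .306 | −.07 to .60 |
| 60 | 2.40 | .020 | .010 | .254 | .214 | .05 to .51 |

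At n = 30 an observed .30 is not significant, narrowly so one-sided. Pooled over 60 it is.

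**The case against.** The strongest defence is that the benchmark is borrowed. The sentence names no power target, the .05 and .80 belong to the primary aims, and determining a correlation need not mean detecting it with 80% power. This is true, and it is why alpha and power are labelled as assumptions. The conclusion does not hang on exactly 80%, however: within a group of 30 the chance of finding a true r of .30 is about one half at best.

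Second, one-sided testing may be the plan's convention. With the equal groups described in the primary power analysis, a two-sample t-test gives 70.5% two-sided against 80.5% one-sided for d = .46 with 60 per group, and 73.4% against 82.7% for d = .35 with 110 per group. The hypotheses are also directional. One-sided, the critical r at n = 30 is .306, so the sentence may simply be a rounded significance threshold. That is plausible, but a true effect sitting at the threshold has only about 50% power.

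Third, the correlations may be meant as pooled. Specific aims supports this for cognitive control: "Patients with better cognitive control are expected to achieve longer durations of abstinence, regardless of treatment assignment". It points the other way for reward response: "Patients who are more sensitive to monetary rewards are expected to achieve longer duration of abstinence, particularly when assigned to a reinforcement intervention". Pooling narrows the gap to about four points one-sided (76% against 80%), and on the significance reading the claim then holds. But the sentence counts participants per group, and pooled power still falls short of 80%.

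Fourth, r ≥ .30 covers larger values. One-sided power at n = 30 is about 81% for r = .45, and pooled two-sided power is about 89% for r = .40. This limits the consequence, but .30 is the value the plan chose to state.

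Last, the adequacy remark in Preliminary studies may only contrast the new sample with the small pilot, and it also covers change over time. Even so, it includes the associations with outcome, so it should not outrun the corrected figures.

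**Conclusion.** The concern holds. At alpha .05, neither sidedness nor pooling brings power for a true r of .30 to 80%. Within a group, such a correlation would be missed about 64% of the time two-sided or 51% one-sided; pooled, about 35% or 24%. The sentence is defensible only if it means that an observed r of .30 is significant and the groups are pooled, and it says neither. The conclusion rests on carrying alpha .05 and 80% power over from the primary aims, and on a single unadjusted correlation with complete data. The consequence is limited: the aim is secondary and exploratory, and the primary comparisons do not depend on it. The sentence should be corrected, but it does not threaten the trial.

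**What to change.** Keep the sample size, scans and planned tests.

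1. In the fMRI part of Data Analysis, replace the sufficiency sentence with the detectable correlations at 80% power and alpha .05: about .49 two-sided (.45 one-sided) within a group of 30, and about .35 two-sided (.32 one-sided) pooled over 60.
2. In the same place, state the alpha, sidedness and power used, and for each planned correlation whether it is within group or pooled.
3. In Preliminary studies, reword the adequacy claim to match.
4. Report each correlation with a confidence interval, so that a non-significant result is not read as evidence of no association.

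The separate sentence on 25 participants after treatment concerns change over time and needs no edit on this account.

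The cost is wording in two places and intervals in the report. The only drawback is that the stated sensitivity looks less favourable.
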